## 5.1 Study Intervention and Pharmacogenomics Testing

- After obtaining the informed consent, two buccal swabs will be collected at least one week prior to the Baseline study visit (the next palliative medicine visit after informed consent). Buccal swabs may be collected by the subject at home or on site.
- Buccal swabs will be transferred to the Levine Cancer Institute's Molecular Biology Laboratory on the same or following day of collection for DNA extraction and genotyping. Subjects who collect samples at home will be instructed to collect and ship overnight only on Monday through Thursday (samples should not arrive at the lab on the weekend or on holiday).
- Genotyping will occur at the Molecular Biology Laboratory for polymorphisms in candidate genes potentially related to pain and depression medications.
- Raw data will feed into an online HIPAA compliant web portal for translation of results into genotype-phenotype data. Each test result will be reviewed by the lab for accuracy of

results and quality control. The laboratory director and/or Sponsor-Investigator (S-I) or sub-investigator if S-I is not available will approve final genotype calls.

- Pharmacists will interpret genotype and phenotype results and translate PGx results into actionable prescribing decisions. Guidelines, including CPIC (<https://cpicpgx.org/>) and FDA (<https://www.fda.gov/medical-devices/precision-medicine/table-pharmacogenetic-associations>), and clinical judgment will be used to make medication recommendations. A test report will be developed for each subject. The pharmacist will send a copy of the report to the referring provider and upload a copy into the medical chart along with a PGx consultation note.
- Subjects will continue to receive supportive care and undergo scheduled study visits throughout the study. Changes to medications can be made during scheduled study visits, on-call visits, or virtually over the phone to mimic standard practice. Providers will be encouraged to refer all study subjects requiring pharmacologic intervention for pharmacy consultation to evaluate PGx results prior to drug prescribing. However, this is not protocol-mandated, and a deviation will not occur if a provider modifies treatment regimens without consulting the pharmacist. The number of pharmacy consults, types of medication recommendations, actionable genotypes, and acceptance rate by the provider will be documented. Data will be collected up to the completion of the Final visit.

### 5.1.1 Schedule of Clinic Assessments

Every visit can occur during a clinic visit (in-person or utilizing virtual care) or over the phone. A subject can be assessed by a trained and delegated Palliative care provider, PharmD, study coordinator, or RN:

- Baseline (day 0) study visit should be no earlier than 2 weeks and no later than 8 weeks from the first ESAS completion.
- A total of 3 subsequent study visits and the Final visit will occur every 4 weeks ( $\pm$  1 weeks) after the Baseline visit. Additionally, non-protocol-directed visits may occur on an as-needed basis (e.g., an emergency due to uncontrolled symptoms).

### 5.1.2 Symptom Assessment Tools

- ESAS ([Appendix A](#)) is a 10-item questionnaire assessing self-reported perceptions of pain, fatigue/energy, nausea, depression, anxiety, drowsiness, appetite, wellbeing, and shortness of breath. Each item is ranked from 0 to 10, with 10 representing the worst symptom. ESAS is routinely performed during all palliative medicine clinic visits.
- PHQ9 ([Appendix B](#)) is a multipurpose instrument for screening, diagnosing, monitoring, and measuring the severity of depression. PHQ9 incorporates depression diagnostic criteria with other leading major depressive symptoms into a brief self-report tool. PHQ9 scores of 0-4 indicate normal or no depression, 5-9 mild, 10-14 moderate, 15-19 moderately severe, and 20-27 severe depression. PHQ9 will be collected for this study, preferably electronically, within 2 business days prior to the study visit or by phone call within 2 business days prior to the study visit. Alternatively, PHQ9 can be collected during a clinic visit on paper.

### 5.1.3 Subject Survey ([Appendix C](#))

The patient survey is intended to assess the subject's perspective of pharmacogenomics testing. The survey will be administered preferably electronically, alternatively over the phone or on paper during a clinic visit at the Final visit time-point or sooner if withdrawn.

If data from ESAS, PHQ9 questionnaires, and Subject survey are missing, when possible, the reason for the missing data will be categorized and documented as follows:

- the subject felt too ill;
- clinician or nurse felt the subject was too ill;
- the subject felt it was inconvenient or took too much time;
- the subject felt it was a violation of privacy;
- the subject didn't understand the actual language or was illiterate;
- administrative failure to distribute the questionnaire;
- other, specify;
- unknown.

## 6. STUDY CALENDAR

### 6.1 Table 2. Study Procedures and assessments

Study Procedures	Registration	Baseline 	Study Visits 	Final Visit 
Informed Consent	X			
Subject demographics 		X		X
Buccal swab collection for genotyping	X 			
Medical/treatment history 		X		
Drug allergies 		X	X	X
PHQ9 		X	X	X
ESAS 	X 	X	X	X
Medication list 		Continuously throughout the study from the Baseline to the Final visit		
Document use of PGx test results 				
Document use of healthcare resource utilization (HCRU) 				
Final visit survey 				X

The Baseline study visit should be completed no earlier than 2 weeks and no later than 8 weeks from the first ESAS completion.

A total of 3 subsequent study visits will occur every 4 weeks ( $\pm$  1 week) after the Baseline visit. The Final study visit will occur 4 weeks ( $\pm$  1 week) after the third completed Study Visit. Subjects will be offered the option to complete study assessments during a clinic visit (in person or virtually) or over the phone.

All the study visits and assessments (including the Baseline visit) can occur during a clinic visit (in-person or utilizing virtual care) or over the phone. Study visits/assessments may be performed by a trained and delegated provider, RN, research coordinator or Pharm D.

Demographics collected during the Baseline visit will be race, ethnicity, insurance status, and zip code. Demographics collected on the Final visit will be annual household income and education level.

Buccal swab collection (Enrollment day) should be performed no later than one week prior to the Baseline study visit (second palliative medicine visit) at the clinic or the subject's home. The specimen may be obtained the same day after the informed consent is signed.

Medical/treatment history: cancer type, stage of disease, ECOG performance status, active chemotherapy, surgery, and radiation therapy within 30 days of the Baseline visit.

Only to medications listed in [Appendix D](#)

Research team will collect PHQ9 prior to the study visit, preferably electronically or by phone, within 2 business days and send them to the Supportive Oncology provider and Sponsor-Investigator. If the response for the PHQ9 question #9 is anything greater than 0, a research designee will contact the applicable LCI social worker. Alternatively, PHQ9 can be collected during clinic visits on paper.

ESAS will be obtained during a clinic visit or utilizing virtual care.

ESAS score done historically visit per standard of care at the initial palliative medicine visit will be collected in the dataset and used for analysis ([Section 11.4.5](#))

Medications listed in [Appendix D](#), currently taken and/or newly prescribed during the visit, and other drugs and/or drug modifications recommended by the pharmacist or provider based on PGx test results outside those in [Appendix D](#) list will be collected every study visit.

Use of PGx test results should be documented any time a drug/dose modification is made (during palliative medicine visits or in between visits).

HCRU (defined as any encounter classified as an outpatient (OP), inpatient (IP), or emergency department (ED) encounter) occurring during the study period will be collected by a research designee. Each encounter will be counted as unique per classification. IP encounters that result from an emergency department presentation will be classified as both an ED encounter and IP encounter. Any encounter lasting longer than 24 hours will be considered an IP encounter. Insurance status and/or type and reason for presentation at each encounter will also be collected.

Survey will be preferably administered electronically (distributed to the subject's email within 30 days after the Final visit). Alternatively, a research designee can collect a survey via paper during the Final visit at the clinic (or sooner if withdrawn) or over the phone as an option.

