### 2.1.3 Exploratory Objectives

- Determine the types & frequencies of actionable genotypes that result in drug/dose selection or modification(s) and those that do not result in drug/dose selection or modification(s).
- Describe the types of new medications prescribed (using medications of interest list; [Appendix D](#)) or medication/dose adjustments based on the PGx results.
- Determine the type & frequency of drug/gene interactions present at the Baseline and the Final study visit using CPIC guidelines and FDA's pharmacogenomics table.
- Summarize PGx best practice advisory alerts among participants enrolled after the transition to Epic to describe the proportion of participants that had a BPA fire in the EMR, the number and type of BPAs per participant, and any actions taken from the BPA.

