### **3.4 Subject Withdrawal**

Subjects MAY be withdrawn from the study for the following reasons:

- More than 8 weeks pass between the completion of ESAS and the Baseline study visit.
- Subject withdraws consent from study procedures. A subject will be removed from the trial at his/her own request. At any time during and without giving reasons, a subject may decline to participate further. The subject will not suffer any disadvantages as a result.
- If, in the Investigator's opinion, compliance with study procedures is compromised and affects the integrity of the trial.
- Death.

Subjects MAY be withdrawn from the study for the following reasons:

- The subject is unable to undergo one or more study visits.
- Use, or suspicion of use, of illicit drugs or substances (i.e., positive urine drug screening) that may, in the opinion of the Investigator, have a reasonable chance of contributing to medication non-compliance
- Developing a concurrent illness or situation that would, in the Investigator's judgment, significantly affect assessments of clinical status and trial endpoints.
- DNA from buccal swabs is not viable, and the laboratory cannot perform PGx testing. Subjects may be asked to provide additional swabs if recollection performed no later than one week prior to the Baseline study visit.

Any subject removed from the trial will remain under medical supervision per standard of care procedures until discharge or transfer is medically acceptable.

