## **5. STUDY PLAN**

The study design is a prospective interventional clinical trial designed to investigate the application of PGx testing to personalize cancer symptom management, particularly pain and depression.

Potential candidates will be presented with consent; screening data for these patients, including ESAS symptom scores, will be captured and used for analysis ([Section 11.4.5](#)). A full waiver of consent and HIPAA for data collection will be requested for the control cohort, which includes patients (with pain  $\geq 4/10$  and/or depression  $\geq 3/10$  who have not been presented with consent and who were presented with consent but decline participation in the study (i.e., do not consent). Study subjects who consent and subsequently screen fail for any reason will also be included in the control cohort. Patients who agree will undergo the informed consent process, and subjects who consent will be screened for eligibility. Those meeting eligibility criteria will be enrolled and undergo buccal swab collection. **Enrollment day** will be considered at the **buccal swabs collection day**. If the collected buccal swabs do not contain enough viable DNA for PGx testing, subjects may be asked to provide additional swabs. No less than 2 weeks and no more than 8 weeks should pass between the first ESAS completion and the date of the **Baseline study visit**. **The Baseline study visit** may be completed during a clinic visit (in person or virtually) or over the phone. It is estimated that PGx results will be available within five business days of swab receipt by the laboratory, and a detailed report will be sent to the clinic. A copy of the test results in PDF (Portable Document Format) format and PGx consultation note will be uploaded to the subject's medical chart. Apart from the availability and use of PGx test results to guide pharmacotherapy, subjects will receive standard of care treatment and undergo ESAS screening during the palliative medicine visits. PHQ9 will be collected by the research team electronically, during the study visit by paper, or by phone. Data, including symptom scores and medications, at each visit, will be captured until the **Final study visit**. Subjects will be asked to complete a short survey within 30 days after the Final study visit to assess their perspectives on PGx testing and the care they received (administered preferably electronically, alternatively via paper during the Final visit at a clinic or over the phone).

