### 7.2 Baseline Procedures

Baseline study visit should be completed no earlier than 2 weeks and no later than 8 weeks from the first ESAS completion during the clinic visits or utilizing virtual care.

- Subject demographics: Race, Ethnicity, Work Status, Insurance Status, Zip code
- Medical history: data related to disease and/or diagnosis, including cancer type, stage of disease, and ECOG performance status
- Treatment history: therapeutic interventions including surgery within 30 days of Baseline, active chemotherapy, active radiation, and active supportive care therapy
- Drug allergies to medications listed in [Appendix D](#)
- ESAS [Appendix A](#) collected as a SOC
- PHQ9 [Appendix B](#) collected preferably electronically within 2 business days prior to the study visit, or alternatively on paper during the clinic visit or by phone call within 2 business days prior to the study visit
- Medications listed in [Appendix D](#), currently taken at the time of Baseline study visit and/or newly prescribed during the visit and, other drugs and/or drug modifications recommended by the pharmacist or provider based on PGx test results outside those in [Appendix D](#)
- Use of PGx to guide/modify pharmacotherapy regimen
- HCRU

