### 7.5.2 Storage of Biospecimens

Specimens will be stored in the Molecular Biology Laboratory only until the pharmacogenomic results have been confirmed by both the Laboratory Director and Sponsor-Investigator (approximately one week from sample receipt). Once PGx results are confirmed by the Laboratory Director and Sponsor-Investigator, all samples will be discarded according to laboratory procedures.

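### Baseline is not timed from release of the PGx report, so the first PHQ9 and the Baseline drug-gene interaction count are not guaranteed to be pre-PGx values

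*Combined protocol and SAP*

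**What the plan says.** **Timing.** Section 5.1.1 states: "Baseline (day 0) study visit should be no earlier than 2 weeks and no later than 8 weeks from the first ESAS completion". Section 5.1 adds that "two buccal swabs will be collected at least one week prior to the Baseline study visit", and Table 2, footnote 5, allows the swab on the day of consent. On results, Section 5 says: "It is estimated that PGx results will be available within five business days of swab receipt by the laboratory". The report and a consultation note then go into the chart (Sections 5 and 5.1). No section makes Baseline depend on that step, and none holds back use of the results until Baseline. Section 5.1 lets drugs be changed at on-call or telephone contacts as well as at scheduled visits.

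**Measurement.** In Table 2 the medication list is collected "Continuously throughout the study from the Baseline to the Final visit", and PHQ9 is first marked in the Baseline column. Section 7.2 defines the Baseline list as Appendix D drugs "currently taken at the time of Baseline study visit and/or newly prescribed during the visit". Section 2.1.3 sets the exploratory objective: "Determine the type & frequency of drug/gene interactions present at the Baseline and the Final study visit". Section 2.2.3 records the interaction count at the same two visits. Section 11.4.5 fits a single-arm mixed model to PHQ9 with a time effect, in support of the Section 2.1.2 objective on how PGx affects outcomes.

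**ESAS differs.** The score from the first palliative visit is kept for analysis (Table 2, footnote 10), so pain and depression on that scale have a value from before the swab.

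**The concern.** A before-and-after description needs a value known to precede the intervention. Here the intervention is the PGx result reaching the people who prescribe. PHQ9 and the interaction count both take their first value at Baseline, whose date is set without reference to that event.

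If a drug is changed on the strength of the report before Baseline, the interaction it removed never enters the Baseline count, and the Baseline-to-Final reduction is understated. PHQ9 works the same way: any benefit or harm from an early change is already in the first score. A second, smaller problem is that the Baseline medication list combines what the subject arrived on with what was prescribed at that visit with results in hand. The plan does not say which of the two defines an interaction present at Baseline.

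**Working it through.** The plan states no figure for the gap between results and Baseline, so there is none to reproduce. The range follows from its own windows.

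**Inputs**
- Baseline: day 14 to day 56 after the first ESAS (Section 5.1.1; Table 2, footnote 1).
- Earliest swab: the day of consent (Table 2, footnote 5). Assumption: consent can fall on the day of the first ESAS, called day 0. The documents do not exclude this.
- Swab to laboratory: same or following day (Section 5.1). Weekend receipt is moved to Monday.
- Turnaround: five business days (Section 5), or about four to five (Synopsis).

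**Formula.** Lead = Baseline day − results day, where results day = swab day + transit + turnaround, in calendar days.

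**Results day for a swab on day 0**
- Same-day receipt, five business days: day 7.
- Next-day receipt on a weekday, five business days: day 8.
- Fastest (Monday swab, same-day receipt, four business days): day 4.
- Slowest (Friday swab, Monday receipt, five business days): day 10.

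**Lead**

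| Swab | Baseline | Central | Range |
|---|---|---|---|
| day 0 | day 56 | 56 − 7 = 49 days | 56 − 10 = 46 to 56 − 4 = 52 days (6.6 to 7.4 weeks) |
| day 14 | day 56 | 49 − 14 = 35 days (5 weeks) | 46 − 14 = 32 to 52 − 14 = 38 days |
| day 0 | day 14 | 14 − 7 = 7 days | 14 − 10 = 4 to 14 − 4 = 10 days |

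Each day that the swab falls after the first ESAS shortens the lead by one day. Section 3.4 lists exceeding eight weeks as a reason a subject may be withdrawn, so the upper limit is not absolute.

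**What can happen during the lead.** Baseline is described as the next palliative visit after consent (Section 5.1; Table 2, footnote 5), so no scheduled palliative visit comes between. The route to an early change is an on-call or telephone contact, which Section 5.1 permits.

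**Which measurements are exposed**
- *Interaction count.* A change made before Baseline is lost. A change made at Baseline is not necessarily lost, because a drug the subject arrived on is still listed as currently taken. It is, however, listed together with new prescriptions chosen with results available.
- *PHQ9.* The preferred collection is within two business days before the visit (Section 5.1.2), so it precedes that visit's prescribing. It is post-PGx only if results were acted on, or discussed with the subject, earlier. Sections 1.2 and 10.1.3 promise counselling on the results without saying when.
- *Primary endpoint.* It records whether a PGx-based selection or modification occurred at any visit with results available (Section 2.2.1). It uses no before value.
- *Matched analysis.* Its outcomes are ESAS pain and depression, and it matches on first-visit scores (Section 11.4.5).

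**The case against.** The strongest reply is that testing ahead of Baseline is the intended design (Synopsis), so a long lead is not a defect and need not mean long exposure. With no scheduled palliative visit in the interval, early changes may be uncommon. The interaction item is exploratory and is to be described qualitatively with summary statistics (Section 11.4.6); no test of change is planned. The PHQ9 model has no control group, and an earlier score would not make it causal. Depression does have a pre-swab measure, on ESAS. Historical prescriptions are to be drawn from the data warehouse (Section 11.4.5).

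All of this stands and limits the importance of the point. None of it supplies a PHQ9 or medication list guaranteed to precede the results: the warehouse prescriptions serve the cost analysis and are not linked to the interaction count.

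A reader might also infer that the one-week minimum between swab and Baseline lets results arrive too late and costs evaluable subjects. The documents do not support that. For a swab exactly seven days before Baseline, the results days above put results between 7 − 4 = 3 days before and 8 − 7 = 1 day after Baseline. The exception is a Friday swab received on Monday (10 − 7 = 3 days after), which requires reading the following day as the following business day. A holiday or slower turnaround would add to this, and Section 7.5.2 puts confirmation of results at "approximately one week from sample receipt". But Sections 2.2.1 and 11.3 count any study visit with results available, and four visits follow Baseline (three study visits and the Final visit). A late result also leaves Baseline cleanly pre-PGx.

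**Conclusion.** The point holds in a limited form. Neither PHQ9 nor the interaction count has a guaranteed pre-PGx value, because results can be in the chart up to about 7 weeks before Baseline. That upper figure assumes a swab on the day of the first ESAS and Baseline at 8 weeks; a day-14 swab gives about 5 weeks. In some subjects the Baseline values may already reflect PGx-guided changes.

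Two stronger conclusions are tempting and should not be drawn. One is that every Baseline value is contaminated: that would need an early change, or early discussion of the results, in every subject, and the documents do not show this. The other is that a stated share of the fall in interactions is hidden: the documents give neither the number of interactions per subject nor the frequency of early changes, so any percentage would be invented.

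The effect is confined to one exploratory description and one uncontrolled secondary model. The correction is a cheap improvement, not a condition for a valid primary result.

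**What to change.** 1. Abstract the Appendix D medication list from the chart as of the swab date, and describe drug-gene interactions at swab date versus Final. In the Baseline list, keep drugs newly prescribed at that visit separate from those already taken on arrival.
2. Send one electronic PHQ9 at Registration, before results are released, with the existing item-9 follow-up (Table 2, footnote 8). Use it as the pre-PGx value in the single-arm PHQ9 model.
3. Reconcile the two recollection statements. Section 3.4 says: "Subjects may be asked to provide additional swabs if recollection performed no later than one week prior to the Baseline study visit". Section 5 allows additional swabs without that condition.

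Day 0 should not be redefined as the first visit after the report. That would make every Baseline post-results and would worsen the problem described here.

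The cost is a short amendment, one extra chart abstraction and one short questionnaire per subject. The medication list can be abstracted retrospectively for subjects already enrolled; a pre-results PHQ9 cannot be recovered once results are out, so that change helps only if made prospectively.

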## 7.4 Final Visit

- The Final study visit will occur 4 weeks ( $\pm$  1 week) after the third completed Study Visit.
  - Drug allergies to medications listed in [Appendix D](#)
  - ESAS [Appendix A](#) collected as a SOC
  - PHQ9 [Appendix B](#) collected preferably electronically within 2 business days prior to the study visit, alternatively via paper during a clinic visit or by phone call within 2 business days prior to the study visit
  - Addition or change in medications listed in [Appendix D](#) and/or dosages, and other drugs and/or drug modifications recommended by the pharmacist or provider based on PGx test results outside those in [Appendix D](#)
  - Use of PGx to guide/modify pharmacotherapy regimen
  - HCRU
  - Patient survey ([Appendix C](#))
  - Subject demographics (part of the final survey): annual household income and education level.

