## **8. REMOVAL OF SUBJECTS FROM STUDY**

### **8.1 Off Study**

Subjects are considered Off Study after completion of the subject survey and the Final visit that occurs 4 weeks ( $\pm$  1 week) after the third completed Study Visit.

Subjects may stop their participation in this study at any time if they no longer wish to participate or if the Investigator believes this to be in the best interest of the subject. When subjects are removed from the study, the reason for study removal and the date the subject was removed should be documented. Other reasons a subject may be removed from study include, but are not limited to:

- Subject non-compliance with study participation, in the opinion of the Investigator
- The subject or legal representative withdraws study consent
- The subject's tumor is confirmed to be a benign per provider
- Buccal swab collected and shipped more than 96 hours after receiving the buccal swab kit or if otherwise deemed non-viable
- The subject unwilling to recollect the buccal swabs if DNA from the first buccal swabs is not viable
- The subject is lost to follow-up
- Investigator's decision to withdraw the subject
- Subject death

Subjects that are Off Study will not participate in any study- related procedures, including data collection.

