## **11.3 Analysis Populations**

Analyses of the primary objectives and secondary objectives concerning counts of PGx-guided drug/dose selections or modifications based on their test results will be conducted on the evaluable population, defined as the population of enrolled subjects with confirmed malignancy (per provider documentation) and completing at least one study visit where PGx results are available (including the baseline visit).

Analyses of secondary objectives concerning the impact of PGx on pain and depression scores will be conducted on the primary evaluable population with valid pain and/or depression scores for at least one post-Baseline Study visit.

Analyses of secondary objectives concerning health care utilizations, costs, and subject survey responses and all exploratory objectives will be conducted on all enrolled subjects.

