Health care utilization (e.g., instances of participant presenting at an emergency department, admitted as an inpatient, any outpatient encounter, or medication prescription) and reason for encounter will be assessed during the study period (starting on the Baseline to the Final study visit) for those undergoing PGx testing. HCRU in year prior to start of study enrollment will be collected for patients from institutional enterprise data warehouse (EDW) via raw billing and medical record data. Insurance status and/or type at each encounter will also be collected. An encounter resulting from another (e.g., ED presentation leading to IP) will be counted separately. Any ED encounter lasting longer than 24 hours will be considered an IP encounter. Diagnosis and procedure codes and priority sequence numbers will be collected from the EDW at least 6 months following study closure to allow for final bills to accrue for HCRU encounters, for those that underwent PGx testing and matched controls. Diagnosis and procedure codes used in billing for each encounter will be used to estimate institutional costs or reimbursement and/or to publicly available sources (e.g., CMS fee schedule) and to obtain patient's historical prescription drugs. Endpoints will be summarized by encounter-level and patient-level data files for frequency of HCRU and descriptive analysis of associated cost. Once data files have been constructed, data will be fit to appropriate statistical analyses and multivariate regression will be employed to interrogate the relationship between costs, resource utilization PGx results, sociodemographic, and clinical patient characteristics. Sensitivity and scenario analyses will be conducted to assess the robustness of model estimates.

Subject responses to survey tool administered at the Final visit (or sooner if withdrawn) will be summarized and described. Regression models may be estimated to describe the association of response and responder characteristic, both univariately and multivariately, adjusted for relevant baseline characteristics.

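### Household income and education are asked only in the end-of-study survey, so they will be missing for subjects who die or are lost first, and any cost regression that uses them may drop those subjects

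*Combined protocol and SAP*

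**What the plan says.** Subject demographics are split between two time points. Table 2, footnote 4 (Section 6.1) says: "Demographics collected during the Baseline visit will be race, ethnicity, insurance status, and zip code". Section 7.2 adds work status to that list. The same footnote continues: "Demographics collected on the Final visit will be annual household income and education level". Section 7.4 gives the instrument: "Subject demographics (part of the final survey): annual household income and education level". In Appendix C they are questions 1 and 2, each with an option to decline. No section gives an earlier routine collection point.

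The survey is preferably electronic and is "distributed to the subject's email within 30 days after the Final visit" (Table 2, footnote 14), with phone and paper as alternatives. Section 5.1.3 allows it "on paper during a clinic visit at the Final visit time-point or sooner if withdrawn". Section 8.1 says that subjects who are Off Study "will not participate in any study- related procedures, including data collection", and it lists death and loss to follow-up among the reasons for removal.

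On the analysis side, Section 11.3 states: "Analyses of secondary objectives concerning health care utilizations, costs, and subject survey responses and all exploratory objectives will be conducted on all enrolled subjects". Section 11.4.5 says that "multivariate regression will be employed to interrogate the relationship between costs, resource utilization PGx results, sociodemographic, and clinical patient characteristics". It does not list the covariates. For missing surveys, Section 5.1.3 asks only that the reason be recorded. No method for missing covariates is given.

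**The concern.** Income and education describe the subject at entry, yet whether they are recorded depends on what happens during follow-up. The population is palliative-clinic cancer patients with substantial symptoms, so some will die or become too ill before the survey. The plan expects this: the missing-data reasons in Section 5.1.3 include being too ill, which plausibly goes with emergency and inpatient use, and language or literacy difficulty, which plausibly goes with education itself.

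The outcome does not depend on returning a survey. Encounters are recorded through the study, and billing codes come from the institutional data warehouse. For a subject who dies in week 8, utilization and cost up to death can be known while income and education cannot. A complete-case model containing either variable would discard a known outcome for want of a fact that could have been asked at entry. The associations would then describe a healthier, more engaged subset than the declared population. Any demographic summary of these two items (Section 11.4.3) would be incomplete for the same people.

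**Working it through.** **The plan's own figures.** The plan gives no rate of attrition to the Final visit and no survey return rate. The nearest figure is 80 enrolled to give 65 evaluable (Section 11.2): 1 − 65/80 = 18.75% not evaluable. It cannot stand in for survey loss. Evaluable means confirmed malignancy plus one visit with PGx results, and that visit may be Baseline (Section 11.3). A subject can be evaluable and never reach the survey.

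**Timing.** Three visits at 4-week intervals, then the Final visit 4 weeks later: 3 × 4 + 4 = 16 weeks after Baseline. The emailed survey may add 30 days (30/7 = 4.3 weeks), so about 20 weeks nominally.

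**Who can have a value under the current text.**

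| Subject | Income and education |
|---|---|
| Reaches Final visit, returns survey | Yes, unless the subject declines to answer |
| Reaches Final visit, does not return email | Possible by phone or paper |
| Withdraws | Possible through the early survey; unclear against Section 8.1 |
| Dies or is lost before the survey | None |

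**Rows lost if either variable is in a complete-case model (illustration).** With assumed missing share a, n = 80 × (1 − a). From sample size alone, standard errors grow by √(80/n).

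| a (assumed) | n | SE factor |
|---|---|---|
| 10% | 72 | 1.05 |
| 20% | 64 | 1.12 |
| 30% | 56 | 1.20 |
| 40% | 48 | 1.29 |

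**Selection (illustration).** Assume that half of the 80 are high users, with 40% missing among them and 20% among the rest. Retained: 40 × 0.6 = 24 and 40 × 0.8 = 32, total 56. High users fall from 50% to 24/56 = 42.9% of the analysed rows.

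Alternatively, with 30% missing and an assumed utilization rate among those missing of 2 times that of completers, mean utilization in the retained rows is 1/(0.7 + 0.3 × 2) = 0.77 of the full-cohort mean. For ratios of 1.5 to 3 at 10% to 40% missing, this runs from 0.95 to 0.56.

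These figures describe who is retained. They are not estimates of bias in a regression coefficient. That bias arises if missingness depends on the outcome after conditioning on the covariates, which is plausible here but cannot be quantified from the documents.

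**The case against.** A reader might infer that everyone who stops early has no value, and that the cost regressions will necessarily become survey-responder analyses. The documents do not support either inference.

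- **Early leavers.** Sections 5.1.3 and 11.4.5 and Table 2, footnote 14 provide for an earlier survey on withdrawal, so some early leavers can supply both items. Section 8.1 does not plainly bar this, because it places Off Study after the survey and the Final visit. Section 11.1, however, dates Off Study at the Final visit, before the emailed survey may arrive. These passages need reconciling. The provision cannot reach deaths or losses.
- **Model content.** Section 11.4.5 names no covariates. Race, ethnicity, insurance status, zip code and work status are due at Baseline, and the regression can be run on those. Rows are lost only if income or education enters. This stands, and it makes the concern conditional.
- **Placement in the survey.** Section 11.4.5 also plans models of survey response on responder characteristics. Those are limited to responders in any case, so the placement costs them nothing.
- **Handling.** The plan does not commit to complete-case fitting, and it promises sensitivity and scenario analyses, though only in general terms.
- **Declining to answer.** Some values would be missing at either time point. Late collection adds loss through death, illness and non-return.

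What remains is that deaths and losses cannot be recovered for these two items, and that the plan has no stated method for the gap.

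**Conclusion.** The point holds in conditional form. Income and education will be absent for subjects who die or are lost before the survey, and may be absent for some who withdraw. If either variable enters the cost and utilization regressions, a complete-case fit departs from the all-enrolled population in a direction plausibly linked to illness and utilization.

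The size cannot be derived from the documents. The 64 to 48 of 80 analysed rests on an assumed 20% to 40% missing, and the shift from 50% to 43% high users rests on further assumptions with no source in the plan.

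The primary proportion, the descriptive utilization and cost summaries, and models restricted to Baseline-collected sociodemographics are unaffected. The point concerns the PGx cohort, since no survey is planned for matched controls. Priority is minor: a cheap improvement to a secondary analysis.

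**What to change.** Move Appendix C questions 1 and 2 to registration or enrollment, with Baseline as a fallback. Amend Table 2 and its footnote 4 and Sections 7.1 and 7.2, and remove the items from Section 7.4 and the final survey. Keep the option to decline. Registration is preferable because enrollment is the day of the buccal swab, at least a week before Baseline, and Baseline collection would miss enrolled subjects lost in between. Ask subjects already enrolled at their next contact.

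In the same amendment, name the sociodemographic covariates in Section 11.4.5, and state how missing covariates will be handled (for example multiple imputation, or a missing category with a sensitivity analysis). Also reconcile the early-survey provision and the emailed-survey timing with the Off Study rules in Sections 8.1 and 11.1.

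The cost is form and protocol wording, with no added visit or procedure. The small downside is that two sensitive questions are asked earlier.
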